Virtual Reality (VR), first coined in 1986 by Jaron Lanier, has expanded from the entertainment industry to clinical medicine in the preceding decades. This is based on its unique ability to replicate scenarios and environments while teaching skills in a potentially cost-effective manner. Simulator training is currently advocated by numerous surgical organizations, including the American Academy of Orthopaedic Surgeons (AAOS) however recent systematic reviews reveal the paucity of literature available for VR training in orthopaedic surgery.^{37,38} Despite this, a recent study highlights the limited interaction of orthopaedic surgeons with VR or simulation experience, though the majority recognizing the role and benefit in practicing procedures and spatial orientation.³⁹ VR utilizes a combination of equipment including a three-dimensional (3D) rendering capable computer, head mounted display (HMD) and controllers with position trackers. Increasingly common is the addition of haptic feedback to VR to recreate sense of touch, vibration and motion.^{38,40} In the field of orthopaedics, VR has demonstrated greatest potential in application for education secondary to the modification in the training environment.²⁸ VR systems provide continuous uninterrupted availability with available mentorship provided through immediate metrics, the ability for repetition, and outcome measures for task completion.

Training a single surgeon in the operating room has been estimated to cost roughly \$48000 in the US. This is partly associated with increased operating room time with surgical trainees present, accounting for approximately 11 184 minutes of operating room time lost per trainee over four years.³⁰ Complications in improper surgical technique, reduction, or implant positioning in orthopaedic trauma surgery has additionally been previously demonstrated. The financial implications are also relevant where surgical inefficiency in Canada ranges from \$621.60 to \$2288.94 CAD per hour in a study incorporating multiple Canadian Hospitals.^{10,41}

We have previously completed a randomized controlled trial of senior (PGY4 and PGY5) orthopaedic residents at the Canadian Shoulder and Elbow Society (CSES) 2019 resident training course. Residents from across Canada were randomized to training using an immersive VR simulator (PrecisionOS Technology, Vancouver, BC, Canada) versus a didactic technical journal article (representing traditional training methods) outlining steps to complex glenoid exposure. In this study, residents trained on VR demonstrated a 570% reduction in training time with equivalent knowledge scores on verbal and written testing, and 150% improvement in cadaveric dissection time with improved instrument handling scores measured by validated Objective Structured Assessment of Technical Skills (OSATS) metrics. This simulator was validated in all domains including transfer of skill and represented the first study of its kind in orthopaedic education (pending publication). This study laid the groundwork for subsequent examinations of transfer of learned skill. Resident education in orthopaedics utilizes multiple media sources for education. Technical surgical videos pertaining to specific implants are frequently read and used by residents and consultant orthopaedic surgeons. Surgical video online resources provide these videos to aid surgeons in developing knowledge of implant specific use. The use of these videos is

pervasive in programs across Canada and the world. We wish to further address the transfer of skill through VR training by comparing it to the well-established use of technical surgical videos in learning implant specific reverse shoulder arthroplasty. Additionally, the efficiency of learning using VR or traditional media systems should be evaluated using validated methods such as transfer of training (ToT) or transfer effectiveness ratios (TER).

PURPOSE AND JUSTIFICATION

Production of an immersive VR suite with haptic and user metric feedback would be an advance over current bench top simulator technology, allowing for greater immersion and interaction, leading to better understanding of surgical planning and implementation. The development of this technology could provide trainees with immersive levels of training not previously seen, with improved learning of technical skills over media such as manufacturer technical documents. The effectiveness of training and efficiency of training of the novel immersive VR training systems need to be evaluated as they are increasingly incorporated into competency based, contemporary residency education.

Research Question: Can immersive VR improve the efficiency and competency of technical skill acquisition in senior orthopaedic surgery residents over technical surgical instructional video in learning reverse shoulder arthroplasty?

Research Objective(s):

Primary: To determine if immersive VR is superior to technical surgical instructional video teaching in acquisition of technical skills in learning reverse shoulder arthroplasty

Technical skill outcomes will be determined by Objective Structured Assessment of Technical Skills (OSATS), a Global Ratings Scale (GRS), and competency assessment (pass/fail) by fellowship trained subspecialty shoulder surgeons

Secondary: (1) To determine the efficiency of learning of immersive VR compared to manufacturer specific technical instructional document training of senior residents in learning reverse shoulder arthroplasty.

1. Efficiency will be determined by transfer of training (ToT) and transfer effectiveness ratio (TER)
2. To validate a created VR scoring system with real-world performance (this will include the use of CT scans of cadaveric specimens)

METHODS

Study Design:

A randomized, blinded intervention-control trial directly comparing immersive VR versus technical surgical instructional video training for teaching of reverse shoulder arthroplasty to senior orthopaedic surgery residents will be conducted.

Residents attending the Canadian Orthopaedic Association (COA), Canadian Shoulder and Elbow Society (CSES) resident training course in Ottawa will be consented for participation. Once consented, residents will be randomized to one of two groups using a computerized blocked protocol based on year of study (R4 and R5) to assure equal level of training between control (technical surgical instructional video) and intervention (immersive VR) groups. Every participant will complete a demographic questionnaire to determine age, handedness, visual correction (eyeglasses), familiarity with shoulder surgery, number of previous courses attended, and familiarity with simulation training and VR. Within the demographic questionnaire will be six questions regarding confidence of performing a reverse shoulder arthroplasty using a modified confidence scale (CS). The demographic questionnaire format will be of Likert-scale responses.

The control group will receive training on completion of a reverse shoulder arthroplasty using a technical surgical instructional video. The control group will be provided as much time as they require to watch the video, including repetition if desired during which they will be timed for completion.

The intervention (VR) group will receive training on completion of a reverse shoulder arthroplasty using an immersive VR simulator (PrecisionOS Technology, Vancouver, BC, Canada). The VR simulator utilizes an HMD producing 3D visuals with haptic controllers for an immersive operating room experience. The module produced consists of the key steps in performing a reverse shoulder arthroplasty using virtual versions of the equipment used in the real procedure. Prior to initiation, participants will be provided with a safety and training demonstration on the use of the VR module by study personnel. The intervention group will similarly be provided as much time as they desire with available repetition as they see fit. The VR group will be timed to task completion as the control group for comparison.

The VR module will provide users with a score based on time to completion of key steps, and performance of key steps such as guide-pin insertion, and overall glenoid baseplate orientation. These positioning scores will be based on clinically relevant cut-off values seen to affect implant longevity. These scores will be subsequently compared to GRS and OSATS scores provided by the assessors for validation purposes.

Both groups will then be taken to a technical skills laboratory where they will be paired with an assessor (fellowship trained, consultant shoulder surgeon and member of CSES). The assessors will be blinded to the training received by the participant. The participants from both groups will then complete a reverse total shoulder arthroplasty using the same equipment used in either the control (technical surgical instructional video) or intervention (VR) learning activity while being assessed on fresh frozen cadavers (scapula to hand). The assessor will use an OSATS, GRS, and overall competency assessment for the resident during the procedure and for evaluation of the finished product. The assessor will also time the resident for time to task completion, which will be determined by the resident when they explicitly express that they are satisfied with final implantation. Following this, participants will complete a survey assessing their enjoyment of learning activity, perceived benefit to continued use in learning orthopaedic skills, and a re-assessment of their confidence following training modality using the modified confidence scale (CS). The post-cadaveric questionnaire format will be of Likert-scale responses.

As part of the procedure, both the assessor and participant will determine implant parameters once the reverse shoulder arthroplasty is complete. The cadaveric specimens with inserted glenoid baseplates will be CT scanned to provide 2D and 3D reformats. This will allow for determination of the implant orientation parameters including version, inclination, rotation, and offset. These parameters will be compared to the VR scores to determine correlation between the VR training and real-world task completion.

Sampling Design and Subject Selection:

Subjects will be recruited from attendance at the Canadian Shoulder and Elbow Society (CSES) annual meeting by volunteering to participate. Subjects recruited will be in their PGY4 or PGY5 years of orthopaedic residency training and will be from multiple Canadian institutions. Once participants are recruited, study personnel will randomize groups to intervention (VR) or control (technical surgical instructional video) groups via a blocked randomization process in statistical computing software R (R Foundation for Statistical Computing, Vienna, Austria).

A recent systematic review comparing validity assessments of surgical orthopaedic simulators demonstrates a breadth of cohort variability, with 17.7% to upwards of 50% differences in reported outcome measures between novice/intermediate and expert groupings. TER ratios have seen variations from 7-42% in early VR simulators for novice surgeons. These studies predominantly focus on VR simulators lacking the immersion of contemporary VR, particularly the system from PrecisionOS.

Similarly, the majority of VR simulator research in orthopaedics pertains to arthroscopic surgery which utilizes different global ratings scale outcome measures. The authors of this proposal have recently completed a similar randomized controlled trial at the 2019 CSES meeting (REB approval obtained from the University of Calgary) comparing senior resident VR training to traditional didactic scientific journal training. This resulted in a significant difference in cadaveric task completion time with n=8 in both groups. This study is presently pending publication and in review. As such, for power determination of comparison of VR trained to control group of novice surgeons utilizing a 2-sided test at 5% significance (alpha = 0.05) and to achieve 80% statistical power (beta = 0.02), considering a representative estimated difference of 25% (which we have seen in our previous study, and is conservative regarding similar literature) in combined outcome measures, six subjects will be required for each cohort.

Inclusion Criteria:

1. Individuals registered in licensed post-graduate orthopaedic residency programs attending the CSES resident course and consenting to participation.

Informed Consent:

There will be no direct patient interaction, therapeutic intervention, or other diagnostic or therapeutic intervention related to patient care. Participants will be provided with a consent form outlining the study. Information gathered on participants will not include direct identifiers aside from demographics of age, gender, and training experience. Questionnaires collected will be de-identified using study codes.

The research demonstrates minimal risk to subjects involved as per TCPS2 Chapter 2, and Chapter 10, as the proposed study is observational, does not allow for direct identification of patients, is not staged, and is non-intrusive.

Study Procedures

Randomization: Subjects will be blocked randomized based on year of study (R4 or R5) using computer software.

Intervention: Study participants will voluntarily complete three questionnaires as well as an activity session utilizing either a technical surgical instructional video or VR to learn reverse shoulder arthroplasty followed by a cadaveric activity in the surgical skills laboratory.

Study Visits: Participants will voluntarily complete study requirements at a single visit during the CSES meeting of which they are electively attending.

Follow-up Visits: No follow-up visits of participating subjects.

Data Collection:

Data collection is prospective following randomization of study participants and blinding of expert raters. Data will be collected in a single setting. Voluntary participants will complete a pre-activity questionnaire identifying age, and gender as well as responses to a number of other questions regarding familiarity with shoulder arthroplasty and surgical simulation/VR as seen in appendix. Post-questionnaire data collected will include questions relating to realism and applicability in learning of the compared modalities and confidence. Questionnaires will be performed during the CSES course on paper/hard copy documents. PrecisionOS, the Lead Researcher, and Co-Researchers will have access to this de-identified data. Hardcopy questionnaires will be retained by the Lead Researcher and kept with PrecisionOS, in a locked and secure office. The hardcopy data will be retained for a period of 10 years. Only designated research personnel will have access to the key to participant de-identified study codes and this will be retained in their locked and secure office. Data will be tabulated to digital format, which will be collected, encrypted and stored on computers owned by the Lead Researcher. This data will then be stored on a secure server. Data will not be transferred out of Canada as per FIPPA. The study will take place once ethics approval is obtained and conclude at the end of the CSES course.

Measures:

Participant specific measures to be collected will include demographics, questionnaire responses, and task completion in an anonymous fashion.

Primary outcome of comparison of VR to technical surgical instructional video teaching will be assessed by OSATS, GRS, and competency grade provided by evaluators during the sawbone session. Secondary outcomes will be determined using the ToT and TER, overall time difference of task completion between groups, and CER. The cadaveric scapula will be assessed for implant version, inclination, rotation, and offset in the glenoid and recorded for each participant using a CT scan.

Data collection sheet including measures assessed can be seen in appendix.

Analytical Plan

Normality testing will be performed via Shapiro-Wilk test with subsequent mean comparative statistics to determine difference between VR and control groups. Descriptive statistics will be conducted. Likert questionnaire responses will be treated as Likert-scale and Likert-type data using descriptive statistics. Reliability testing for outcome scales in determining internal consistency will be assessed by Cronbach's alpha.

Ethical considerations

Potential Benefits: Study participants will receive expert instructional information regarding shoulder arthroplasty by participating. No remuneration for participation will occur. Longitudinal benefits could include improved technical skills in reverse shoulder arthroplasty.

Potential Risks: No direct risks to study participants involved. Subject recruitment is free of coercion, and only de-identified demographic data used with adherence to FIPPA and TCPS2 guidelines for data handling and storage.

Subject Safety Provisions: No direct risks to study participants. Occasionally use of immersive VR can produce feelings of nausea. This will be dictated to study participants prior to commencing the study, and participants are free to withdraw at any time. Safety provisions include data handling and transfer of patient information with adherence to FIPPA and TCPS2 guidelines and all attempts to store and utilize de-identified data.

Ethics Approval: Fraser Health Research Ethics Board (REB); Calgary REB

Plans for Publication and conference presentations:

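### ToT and TER are undefined and have no untrained reference; on the conventional formula, a VR-versus-video TER leaves out the video arm's recorded training time

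*Combined protocol and SAP*

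**What the plan says.** Under Research Objective(s), the first secondary aim is comparative: "To determine the efficiency of learning of immersive VR compared to manufacturer specific technical instructional document training of senior residents". The measures are then named: "Efficiency will be determined by transfer of training (ToT) and transfer effectiveness ratio (TER". The Measures section repeats them: "Secondary outcomes will be determined using the ToT and TER, overall time difference of task completion between groups, and CER".

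No section gives a formula, numerator, denominator or reference group for ToT, TER or CER, and the Analytical Plan mentions none of the three. The reference is not even named consistently: the objective speaks of an instructional document, whereas under Study Design "The control group will receive training on completion of a reverse shoulder arthroplasty using a technical surgical instructional video".

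On the design: "residents will be randomized to one of two groups using a computerized blocked protocol based on year of study (R4 and R5". Both groups are trained and both set their own pace. Control residents have "as much time as they require to watch the video, including repetition if desired during which they will be timed for completion". For the other arm, "The VR group will be timed to task completion as the control group for comparison". Each resident then performs one cadaver procedure, timed by the assessor, and everything happens at a single visit. There is no untrained arm and no cadaver attempt before training.

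**The concern.** On the usual convention, which is an assumption here because the plan gives none, ToT and TER describe how much real-task time prior training saves against no prior training. TER divides that saving by the training time spent. This trial never observes a resident without training. The natural substitute is to put the video arm in the place of the untrained group. The ratio then contains the VR arm's training time but not the video arm's.

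At stake is the efficiency conclusion. The objective is to compare two ways of training, and the time each takes to deliver is half of that comparison. A ratio that holds only one of the two training times can look favourable when VR costs more time overall. It can also show nothing when VR saves time: if cadaver times are equal and VR trains faster, TER is zero. The omitted term may be large. The background reports that in the previous trial, against a journal article, VR cut training time by 570%. A reduction cannot exceed 100%, so the figure cannot be turned into minutes, and the comparator was different, but it points to a wide gap between arms. Without a stated formula, the choice of measure could also be made after the data are seen.

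**Working it through.** **Inputs from the plan.** Two trained arms, with training time and one post-training cadaver time per resident in both (Study Design). No ToT or TER target is stated for this trial, so there is no plan figure to reproduce. No session length is stated either, so every number of minutes below is an assumption.

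**Notation and assumed formulas.** Cadaver time: Tu untrained, Tc video, Tv VR. Training time: xc video, xv VR. Against a reference time R:

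- ToT = (R − T) / R
- TER = (R − T) / x

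**Assumed values.** Tc = 60 min, Tv = 45 min, xv = 40 min. The cadaver gap is 15/60 = 25%. This borrows the size of the difference in the sample-size paragraph, which refers to combined outcome measures and not to time.

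**1. Absolute transfer (R = Tu).** Take xc = 20. VR TER = (Tu − 45)/40 and video TER = (Tu − 60)/20.

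| Tu (min) | VR TER | Video TER |
|---|---|---|
| 60 | 15/40 = 0.375 | 0/20 = 0 |
| 75 | 30/40 = 0.75 | 15/20 = 0.75 |
| 90 | 45/40 = 1.125 | 30/20 = 1.50 |

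The order of the arms reverses at Tu = 75, and the trial does not measure Tu. Neither arm's own TER can be estimated, and their ranking cannot be inferred.

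**2. VR relative to video (R = Tc).** ToT = 15/60 = 25% and TER = 15/40 = 0.375. Neither contains xc. Total VR time is 45 + 40 = 85 min.

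| Video training xc (min) | TER | Video total (min) | Total saved by VR (min) |
|---|---|---|---|
| 5 | 0.375 | 65 | −20 |
| 20 | 0.375 | 80 | −5 |
| 40 | 0.375 | 100 | +15 |
| 60 | 0.375 | 120 | +35 |

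The sign changes at xc = 25 min (60 + 25 = 85), and TER does not move.

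**3. A ratio that uses both training times.** Cadaver time saved per extra training minute is (Tc − Tv)/(xv − xc). It gives 15/35 = 0.43 at xc = 5 and 15/20 = 0.75 at xc = 20. It is undefined at xc = 40 and gives 15/(−20) = −0.75 at xc = 60, where VR is quicker on both counts. It can be calculated, but it is awkward to report when training times are close or VR trains faster.

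**4. Fit with the Analytical Plan.** The numerator of a relative TER is itself a difference between arms. It yields one value for VR and none for video, so the planned comparison of group means has no pair of TERs to compare.

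**The case against.** The strongest reply is that the plan states no formula, so the missing video training time is a property of the convention and not of the plan's text. That stands as to wording: what the documents show is that the measures are undefined. But if the convention is not meant, the plan must say what is.

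A reader might go further and infer that the efficiency objective cannot be answered, or that the defective ratio is the only one available. The documents do not support either. The objective asks about VR relative to other training, not about absolute transfer. Training time is recorded in both arms expressly so that they can be compared, and cadaver time is recorded in both. A relative ToT, an incremental ratio and direct time differences can all be calculated.

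A reader might also infer that no planned measure combines training and cadaver time. That is not established. The plan applies the idea of task completion to the training session as well as to the cadaver procedure, so the overall time difference listed under Measures may cover both. CER is undefined and may also bear on it.

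Three further objections stand in part:

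- **Total time is a value choice.** It counts a minute of self-paced training as equal to a minute of operating. The background argues from the cost of operating-room time, so 85 against 80 min does not by itself make VR less efficient. Total time should therefore not be the sole replacement.
- **The minutes are hypothetical.** They show how the formula behaves and do not forecast the result.
- **The TERs of 7–42% from early simulators are only background.** The plan does not say it will compare against them. The point here is a caution on labelling.

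**Conclusion.** The concern holds in a limited form. ToT and TER are named as the efficiency measures without a formula or reference group, in a trial with no untrained residents and no baseline attempt. Assuming the conventional definitions, absolute transfer is out of reach for both arms. A VR-versus-video TER cannot tell a training method that costs more total time from one that costs less: in the illustration it stays at 0.375 while the total time saved by VR runs from −20 to +35 min. This is more than missing detail, because applying the named measures to the trial's own control would produce that ratio. It is less than a failed objective: the relative question remains answerable from data already to be collected. The point concerns a secondary outcome and leaves the primary comparison untouched. It should be settled before analysis.

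**What to change.** In the Secondary objective and in Measures, with a matching line in the Analytical Plan:

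1. Give the formulas for ToT and TER, state that the reference is video-trained residents, and use that comparator in the objective. Label both as descriptive. Say that they do not measure absolute transfer and are not on the scale of the cited 7–42% TERs.
2. Base the efficiency comparison on the between-arm difference in training time and the between-arm difference in cadaver time, each with a 95% confidence interval. Add their sum, total time per resident, as a further summary, and show all of these beside OSATS and GRS.
3. State whether the overall task-completion time difference includes training time.
4. Define CER or remove it.

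The cost is wording only, since both times are already to be recorded in both arms. There are two downsides. The result will not be on the published TER scale. Total time also weights training and operating minutes equally, which is why the two components are shown separately. With the planned six residents per arm the intervals may well be wide, and reporting them makes that visible.

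### No random or arm-balanced pairing of residents with assessors is specified, and the analysis has no assessor term, so differences in assessor severity are left uncontrolled

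*Combined protocol and SAP*

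**What the plan says.** The Study Design section describes the cadaver assessment. "Both groups will then be taken to a technical skills laboratory where they will be paired with an assessor", who is a fellowship-trained shoulder surgeon. "The assessors will be blinded to the training received by the participant". The same person gives every grade: "The assessor will use an OSATS, GRS, and overall competency assessment for the resident during the procedure and for evaluation of the finished product". The Measures section makes those grades the primary outcome, which "will be assessed by OSATS, GRS, and competency grade provided by evaluators".

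Allocation to arm takes account of training year only: "Subjects will be blocked randomized based on year of study (R4 or R5) using computer software" (Study Procedures, Randomization). The Analytical Plan reads: "Normality testing will be performed via Shapiro-Wilk test with subsequent mean comparative statistics to determine difference between VR and control groups". Its one reliability measure is this: "Reliability testing for outcome scales in determining internal consistency will be assessed by Cronbach's alpha".

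The supplied text does not give the number of assessors, the number of residents per assessor, how pairs are formed, any double rating or calibration, or any role for assessor in the analysis. The data collection sheet is in an appendix that was not supplied, so whether it records assessor identity is unknown.

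**The concern.** Surgeons differ in how strictly they grade. If one assessor grades several residents, those grades share that assessor's severity. If the assessors who saw the VR residents are not the ones who saw the video residents, the difference between arms contains the difference between assessors, and a comparison of means cannot separate the two.

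Two features of the plan might seem to cover this, but neither does. Blinding prevents grading that depends on arm; it leaves severity unchanged. Cronbach's alpha describes how items within a scale agree, not how assessors agree.

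The plan also leaves open a route by which pairing could follow arm. Both groups train for as long as they wish and then go to the laboratory. If training times differ by arm, residents of one arm could arrive first and fill the first available assessors. Data are collected at a single visit, so an unfortunate pairing could not be repaired afterwards.

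**Working it through.** **Inputs from the plan.** Six residents per cohort, two-sided 5% test, 80% power, estimated difference of 25% (Sampling Design and Subject Selection).

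**Assumed inputs.** The share of score variance due to assessor (ICC) is 0.3, with a range of 0.1 to 0.5. The number of assessors is varied. Total score variance is set to 1.

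**1. The plan's own figure.** No SD is given, so six per cohort can be neither confirmed nor refuted. Six per arm has 80% power for a standardised difference d of 1.62 by the normal approximation or 1.80 by the t-test (noncentral t, 10 df). If the 25% means 25 points, the implied SD is 25/1.62 = about 15.5 or 25/1.80 = about 13.9 points. I use d = 1.796 as the effect that the unblocked t-test detects with 80% power.

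**2. How large a spurious difference can be.** If k assessors grade each arm and none grades both, the assessor contribution to the arm difference has SD √(2 × ICC / k). At ICC 0.3:
- one per arm: √0.6 = 0.77 score SD
- three per arm: √0.2 = 0.45 score SD

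**3. False-positive rate of the unadjusted t-test.** Simulated, 6 v 6, no true effect, 200,000 trials per cell.

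| Pairing | ICC 0.1 | ICC 0.3 | ICC 0.5 |
|---|---|---|---|
| One assessor per arm | 11.5% | 26.6% | 42.0% |
| Two per arm, each one arm only | 7.3% | 13.3% | 20.2% |
| Three per arm, each one arm only | 6.1% | 8.9% | 12.3% |
| Two assessors, split 5+1 and 1+5 | 7.3% | 12.2% | 18.5% |
| Six assessors, four single-arm, two mixed | 5.5% | 6.4% | 7.5% |
| Two assessors, split 4+2 and 2+4 | 5.2% | 5.1% | 4.8% |
| Three assessors, split 3+1, 2+2, 1+3 | 5.0% | 4.7% | 4.2% |
| A different assessor for each resident | 5.0% | 5.0% | 5.0% |

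When three or six shared assessors are paired at random, the rate is also about 5% (checked for ICC 0.1 to 0.4). Substantial inflation therefore needs complete or nearly complete separation of assessors by arm.

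**4. Power when assessors are balanced and fitted as a block.** The noncentrality is d√3 / √(1 − ICC). With three assessors grading 2 + 2 there are 12 − 1 − 3 = 8 df. With six grading 1 + 1 there are 12 − 1 − 6 = 5 df. The reference is 80% for the unblocked test.

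| Design | ICC 0 | ICC 0.1 | ICC 0.2 | ICC 0.3 |
|---|---|---|---|---|
| Three assessors, 2 + 2 | 78% | 82% | 86% | 90% |
| Six assessors, 1 + 1 | 70% | 75% | 79% | 84% |

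Type I error is about 5% throughout when the block is fitted.

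**5. Balancing without the model term.** With three balanced assessors and an ordinary t-test, type I error is 4.3% at ICC 0.1 and 3.0% at ICC 0.3. The test becomes conservative, so the schedule and the model term belong together.

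**6. Pass/fail.** An exact test stratified by assessor can still reach significance. With three assessors grading 2 + 2, the most extreme table has two-sided p = 2 × (1/6)³ = 0.009. With six grading 1 + 1 it is 2 × (1/2)⁶ = 0.031.

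**The case against.** The strongest objection is that the documents are silent on pairing, and silence is not a flawed design. A reader might infer that assessors will be divided by arm, or that the trial runs at a 9% to 27% false-positive rate. The documents support neither. Being paired with an assessor can mean one to one, and then the t-test keeps its level and no assessor term can be fitted. The text takes both groups to the laboratory and collects data in a single setting; it does not describe the arms arriving separately. A lean towards one arm, the more plausible result of self-paced training, mostly causes no inflation. Nor does the plan say that ratings will be treated as independent. It refers to "subsequent mean comparative statistics to determine difference between VR and control groups" and names no test.

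This stands, and it makes the inflation figures conditional. It does not remove the point. Nothing in the plan rules out pairing by arm. Even with random pairing, severity adds avoidable noise, and with six residents per arm a chance imbalance can shift the single estimate.

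A second objection is cost. Blocking uses degrees of freedom, and an assessor who grades during the procedure and times it must take residents in turn. This also stands, and it is counted under the fix.

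**Conclusion.** The concern holds in conditional form. The plan specifies no random or arm-balanced pairing and no assessor term, while all three primary measures depend on a single assessor's judgement.

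At an assumed ICC of 0.3, the false-positive rate is about 9%, 13% or 27% under complete separation with three, two or one assessors per arm, and 12% for a 5+1 / 1+5 split. Under milder clustering it is close to 5%, with 6.4% the highest of the milder patterns tried. Under random pairing or one assessor per resident it is about 5%, and severity is then noise or chance imbalance in a 12-person trial. These figures rest on assumed values for the ICC and the number of assessors, and on normally distributed severity.

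This should be changed before the session because the remedy is cheap and cannot be applied afterwards. It is not evidence that the planned comparison is invalid as it stands.

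**What to change.** Before the laboratory session:

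- Have a person who does not grade allocate residents to assessors at random within arm. Wherever an assessor grades more than one resident, that assessor should grade equal numbers of VR and video residents in random order (for example 2 + 2 with three assessors). Keep the list from the assessors so that blinding holds.
- Record assessor identity for every grade.
- Analyse OSATS and GRS by arm with assessor as a block. Compare pass/fail within assessor with an exact stratified test.
- If every resident must have a different assessor, allocate assessors to residents at random and fit no assessor term.

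**Cost.** A schedule and one model term. With three assessors, power is 78% rather than 80% if assessors do not differ, and 82% to 90% at ICC 0.1 to 0.3. With six assessors as fixed pairs, power is 70% to 79% at ICC 0 to 0.2, so fewer assessors with more residents each are preferable where the session allows. Assessors who grade several residents must do so in turn, up to four procedures each in the 2 + 2 design. That lengthens the session and varies the delay between training and test. Random order within assessor keeps the wait for an assessor unrelated to arm.
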